**1.INTRODUCTION/ REVIEW:**

Non-intubated Video-Assisted Thoracoscopic Surgery (nVATS), requires an increased anesthesiological effort, accurate patient selection and rigorous planning of airway management in that a switch to general anesthesia and lung separation becomes necessary. Lung separation is obtained with the induction of a surgical pneumothorax, although emphysema and pleural adhesions can slow down the resulting lung collapse (*Deng et al., 2016*).

The reasons for preference of awake patient includes; preservation of diaphragmatic activity besides avoidance of several complications related to general anesthesia such as; deterioration in respiratory functions (like atelectasis, ventilator-induced lung injury, diminished functional residual capacity leading to difficult weaning from mechanical ventilation), impaired cardiac performance and reduced postoperative nausea and vomiting. Lastly, a diminished recourse to anesthetic drugs help the preservation of hypoxic pulmonary vasoconstriction (*Chen et al., 2012*).

The main aim of TEA is to block somatosensory and motor fibers between T1-8 while keeping spontaneous breathing. During procedure, TEA in nVATS patients provided a good preservation of pulmonary functions which are reflected in arterial blood gas values. This can be justified by the increase in diaphragmatic shortening and increased functional residual capacity (FRC). (*Sagiroglu et al., 2018*).

On the downside, paradoxical breathing (Pendelluft effect) can develop between the two lungs, increasing the risk of hypoxemia and hypercapnia, sometimes so evident to require a switch to general anesthesia, in 1% of patients. In most cases, hypercapnia resolves spontaneously, and postoperative PaCO2 is actually lower than after conventional anesthesia. Moreover, permissive hypercapnia can have positive results on the general outcome. Hypotension, due to the mediastinal shift that occurs during pneumothorax, is a potential issue, but it does not appear to be more relevant than under general anesthesia (*Pompeo et al., 2015*).

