In the anesthesia clinic, an informed written consent will be taken from every patient one day before the surgery. The VAS will be explained to the patients. Anesthesia will be provided according to the hospital protocol in respect to preoperative investigations, fasting hours and intra-operative monitoring and drugs.

- **Study Interventions:** The study will include 60 patients fulfilling the inclusion criteria. They will be randomized into 2 equal groups by a computer generated random numbers table, each consisting of 30 patients, namely group A and group B.

- **Group A:** Awake Patients will receive sole Thoracic Epidural Anesthesia.

- **Group B:** Patients will receive General Anesthesia with one lung ventilation.

Preoperatively, Intravenous access will be established and lactated ringer solution will be infused. Monitors for non-invasive blood pressure, heart rate, electrocardiogram (ECG), pulse oximetry (SpO2), and capnography for end tidal CO2 (ETCO2). Invasive arterial line is inserted for serial perioperative ABGs

Patients will be observed for any complications either related to the procedure e.g: hematomas or related to drugs injected e.g: hypotension, bradycardia, hypoxemia, nausea, vomiting or any other adverse effects and will be managed.

- In case of hypotension (drop of blood pressure >20% of baseline reading), 10-30mg of ephedrine diluted over 10ml normal saline 0.9% will be given intravenously by titration according to the blood pressure.
- In case of bradycardia, when it is associated with hypotension or any signs of impaired perfusion, 0.5mg of atropine will be given and can be repeated every 3-5min with a maximum of 3mg.
- In case of fall in peripheral SpO2, supplemental oxygen will be given to keep SpO2 above 94%.

- In case of postoperative nausea and vomiting (PONV), ondansetron 4mg diluted in 10ml normal saline 0.9% will be given intravenously slowly over 10 min.

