Patients in thoracic epidural anesthesia (TEA) group will pre-medicated using midazolam 3-4 mg intravenous (IV) and fentanyl 50 mcg IV. Then patients will placed in the setting position. Under aseptic precautions, skin infiltration with local anesthesia will be done using a 5ml syringe containing 5ml of 1% lidocaine. An epidural catheter will be inserted between T3—T4 and T4—T5 for thoracic procedures meeting the inclusion criteria. A test dose (5 ml) of 2% lidocaine will be given, followed by 15-20 ml of bupivacain 0.5% and 50 mcg of fentanyl. The objective is to achieve sensory and motor block between C7 and T7 levels. At this level diaphragmatic respiration is maintained. In case of persistent hemodynamic instability or persistent hypoxemia, the patients will be transferred to the other group.

Patients will receive general anesthesia (GA) as follows, after proper assessment of the airway and anticipation of difficult airway, all patients will receive premedication in the form of 3-4 mg midazolam IV, ranitidine 50 mg IV as H2 receptor antagonist, metoclopramide 10 mg IV and dexamethasone 4 mg IV as post-operative nausea and vomiting (PONV) prophylaxis. Start preoxygenation with 100% O2 on 8 L/min for 3 min via face mask. Induction of anesthesia with propofol (2mg/kg) and fentanyl (1 mcg/kg). Tracheal intubation and double endotracheal tube insertion will be facilitated with cisatracurium 0.1 mg/kg. and confirmation of it is position will made by fiberoptic bronchoscopy, Anesthesia will be maintained with isoflurane (1-2 %) and cisatracurium (0.05 mg/kg per dose). After the end of the operation, anesthesia will be discontinued, and extubation of the patient will be done after full neuromuscular recovery after reversal of muscle relaxant by neostigmine (0.05 mg/kg) and atropine (0.02 mg/kg).

Postoperative pain and opioid consumption will be assessed after regaining of sensation using the VAS. Post-operative analgesia will be offered in regular doses of Paracetamol 1gm IV every 6 hours for the following 48 hours. Rescue analgesia will be given when VAS  $\geq$ 3, in the form of an injection of Pethidine 50 mg diluted in 10ml normal saline 0.9%, to be given intravenously slowly over 10 min.

- **Measured outcomes**

- **Primary outcome:**

Perioperative changes in blood gases [ Time Frame: Immediately before operation, intraoperatively per hour, and postoperatively per 2 hrs till 24h ]

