Ratio of arterial oxygen tension to fraction of inspired oxygen (PaO2/FiO2), arterial carbon dioxide tension (PaCO2). Hypoxemia is defined as peripheral oxygen saturation (SpO2) < 92% on room air with a need for oxygen supplementation.

- **Secondary outcomes:**

- Postoperative pain using the Visual Analogue Scale (VAS), [ Time Frame: Postoperatively at 3h,12h and 24h ].
- Postoperative opioid (Pethidine) consumption [ Time Frame: Postoperatively during the 24h after regaining of sensation ].
- Hospital stay [ Time Frame: from day of operation to discharge; average, 5 days ]
- Perioperative changes in cardiocirculatory variables including heart rate (HR) and mean arteial pressure (MAP) [ Time Frame: Immediately before the operation, intraoperatively per hour, and postoperatively per 2 hrs till 24h ]
  - Bradycardia is defined as:  $HR \leq 50$  bpm
  - Hypotension is defined as a decrease in systolic blood pressure  $>20\%$  of basal.
  - Hypertension is defined as an increase insystolic blood pressure  $>20\%$  of basal.
- The onset of ambulence. Rate of occurence of falling after ambulence will be recorded in each group. [Time Frame: During the 24 hours after regaining of full motor power].
- Number of episodes of PONV [Time Frame: During the 24 hours postoperatively].
- **Statistical Analysis:** The collected data will be revised, coded and introduced to a PC using statistical package for social science (SPSS 15.0.1. for windows; SPSS Inc, Chicago, IL, 2001).
 

Data will be presented as mean and standard deviation (+- SD) for quantitative parametric data, median and range for quantitative non-parametric data and as numbers and percentage for qualitative data. Suitable analysis will be done according to the type of data obtained.  $P < 0.05$  will be considered significant.

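### The rule moving failed epidural patients to the other group can be read as reassigning randomised patients, and no analysis population is named to rule that out

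*Combined protocol and SAP*

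**What the plan says.** All references are to the combined protocol and SAP.

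- **Methodology, Study Interventions.** Patients are "randomized into 2 equal groups by a computer generated random numbers table, each consisting of 30 patients, namely group A and group B". Here a group is a randomised arm. Group B is described by its treatment: "Patients will receive General Anesthesia with one lung ventilation".
- **Methodology, epidural technique.** The paragraph on the epidural arm ends: "In case of persistent hemodynamic instability or persistent hypoxemia, the patients will be transferred to the other group". The next paragraph opens the general-anesthesia regimen: "Patients will receive general anesthesia (GA) as follows". No rule describes a move from Group B to Group A.
- **Methodology, Measured outcomes.** The primary outcome is "Perioperative changes in blood gases", specified as PaO2/FiO2 and PaCO2; hypoxemia is defined in the same place. Heart rate and mean arterial pressure are a secondary outcome.
- **Methodology, Statistical Analysis.** The only statement on method is "Suitable analysis will be done according to the type of data obtained". There is no analysis population, no intention-to-treat or per-protocol rule, and no handling of patients who change technique.
- **Introduction.** A change of technique is mentioned twice: "rigorous planning of airway management in that a switch to general anesthesia and lung separation becomes necessary", and, for hypoxemia and hypercapnia, "sometimes so evident to require a switch to general anesthesia, in 1% of patients".

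**The concern.** If the sentence is applied as written, a patient randomised to the epidural who does badly on oxygenation or hemodynamics becomes a Group B patient. The arms compared at the end would then be defined partly by what happened after randomisation, through events close to the primary outcome and one secondary outcome. Randomisation no longer protects such a comparison. The plan neither adopts this analysis nor excludes it.

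The same gap remains if the sentence means only a change of anesthetic. Nothing says whether a converted patient, or the blood gases taken after conversion, count in Group A or Group B. At stake are the validity of the main comparison and, because feasibility is a stated aim, the visibility of epidural failures.

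**Working it through.** **Inputs from the plan.** Arm size: the plan gives 40 in total, 40 per group and 60 in total, so n = 20, 30 and 40 per arm are all used. Sample-size figures for PaO2 change: awake -3 (SD 1.5), comparator -6.5 (SD 1.83) mmHg, alpha 0.05, power 100%. Switch rate: 1%, respiratory reasons only; no rate is given for hemodynamic instability.

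**Assumptions, not in the plan.** Transfer rates of 5% and 10%; correlation rho between trigger and endpoint of 0, 0.5 or 1; two-sided test; higher values better; a single endpoint per patient; moved patients keep their own values.

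**1. The plan's own figure.** Pooled SD = sqrt((1.5² + 1.83²)/2) = 1.673 mmHg; difference = -3 - (-6.5) = 3.5 mmHg. Power is 0.999998 at 20 per arm and above 0.999999 at 30 and 40. The stated 100% is reproduced at each arm size.

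**2. Chance that the rule operates at 1%.** P(at least one transfer) = 1 - 0.99^n = 18%, 26% and 33% for n = 20, 30 and 40. No transfer is the most likely result (82%, 74%, 67%).

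**3. Analysis by resulting group, no true effect.** Suppose the fraction p of Group A with the lowest trigger values moves to B. Let f be the standard normal density at its p-quantile. In SD units, the patients left in A average rho·f/(1-p), and the enlarged B averages -rho·f/(1+p). Hence

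bias = rho × 2f/(1 - p²).

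| p | f | bias, rho 0.5 | bias, rho 1 |
|---|---|---|---|
| 1% (documented) | 0.0267 | 0.03 SD | 0.05 SD |
| 5% (assumed) | 0.1031 | 0.10 SD | 0.21 SD |
| 10% (assumed) | 0.1755 | 0.18 SD | 0.35 SD |

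Simulation at the three arm sizes (100,000 replicates per scenario, pooled t-test) agrees. It also covered a variant in which a binomial number of lowest-ranked patients moves. Across both models and rho 0.5 to 1:

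- 1%: bias 0.02-0.05 SD, type I error 5.0-6.1%.
- 5%: bias 0.08-0.21 SD, type I error 6.0-15.6%.
- 10%: bias 0.16-0.35 SD, type I error 8.0-33.7%.
- rho = 0: no bias, type I error 4.9-5.1% at all three rates.
- Analysed as randomised: 4.9-5.1% throughout.

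**4. Analysis by resulting group, with the plan's 3.5 mmHg effect.** Moved patients now also bring Group A's higher mean into B, which lifts the mean of B by 3.5p/(1+p). Hence

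shift = 1.5 × rho × 2f/(1 - p²) - 3.5 × p/(1 + p) mmHg.

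- p = 1%, rho 0: -3.5 × 0.01/1.01 = -0.035 mmHg; divided by 1.673, -0.02 SD.
- p = 1%, rho 1: 1.5 × 0.0533 - 0.0347 = +0.045 mmHg, or +0.03 SD.
- p = 10%, rho 0: -3.5 × 0.10/1.10 = -0.318 mmHg, or -0.19 SD.
- p = 10%, rho 0.5: 1.5 × 0.1773 - 0.3182 = -0.052 mmHg, or -0.03 SD.
- p = 10%, rho 1: 1.5 × 0.3545 - 0.3182 = +0.214 mmHg, or +0.13 SD.

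Simulation agrees with these values to about 0.01 SD, and power stays at or above 99.9% in every scenario. These figures are for PaO2, whereas the listed primary outcome is PaO2/FiO2 and PaCO2. They show that the direction depends on the true effect; they are not a forecast.

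**The case against.** The strongest reply is that the sentence is a clinical instruction. It stands in the epidural technique, not in the statistical paragraph. The Introduction speaks of switching to general anesthesia, Group B is described by its treatment, and the general-anesthesia regimen follows at once. On that reading, the absence of a rule from B to A is what one would expect and is no separate defect. This stands as a plausible reading, but the analysis question stays open under it too.

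It is also fair that the harm is conditional. It needs analysis by resulting group, which the plan does not state, and at 1% it is small. The exclusion criteria remove hemodynamically unstable, hypoxemic and hypercarbic patients. Hypotension and falling saturation are treated first, and only persistent events trigger the move. All of this stands.

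Three stronger readings are tempting and not supported:

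- **That the plan commits to analysing patients in the group they end up in.** It does not say so; it is silent.
- **That the bias necessarily favours the epidural, or that transfers unrelated to an endpoint are harmless.** Both hold only with no true effect. With the plan's own difference, unrelated transfers dilute it, and the net shift can have either sign.
- **That type I error could be expected to reach about a third.** That value needs an assumed 10% rate, 40 per arm and rho = 1, which makes the trigger identical to the endpoint although one trigger is hemodynamic. The plan gives no such rate.

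Nor is the lack of a conversion count an error: complications are already observed and an anesthetic sheet is already a study tool.

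**Conclusion.** The point holds in limited form and should be fixed. Two things are certain: the wording, which taken literally moves patients between randomised arms after randomisation on outcome-related triggers, and the absence of any analysis population to override it. Whether reassignment is intended is not settled by the documents.

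The size and direction of any bias are left open. At the only documented rate the shift is 0.02-0.05 SD toward the epidural with no true effect and a related trigger, and about -0.02 to +0.03 SD under the sample-size effect. Larger shifts rest on assumed rates and correlations. The case for acting does not depend on them, because analysis as randomised keeps type I error at about 5% in every scenario examined.

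**What to change.** Leave the clinical decision to convert unchanged. Reword the sentence so that it describes a change of anesthetic and does not reassign the randomised group. Add to Statistical Analysis: *Patients converted to general anesthesia remain in Group A for all analyses (as randomised); scheduled measurements continue and are included in Group A.* A per-protocol analysis, if wanted, should be a sensitivity analysis only, because it drops the epidural failures.

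As a useful addition given the feasibility aim, report the number of Group A patients converted, with reasons.

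Cost: one reworded sentence, one analysis-set sentence, one reporting line and one field on the existing anesthetic sheet; no extra blood sampling. Downside: the estimated epidural effect may be slightly diluted, because measurements taken after conversion count in Group A.

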## 3.METHODOLOGY:

### Patients and Methods:

- **Type of Study:** Prospective randomized clinical study.
- **Study Setting:** This study will be conducted in Ain Shams University Hospitals..
- **Study Period:** Expected for two years starting from 2019.
- **Study Population:**
  - Inclusion Criteria:*
    - ASA less than or equal II.
    - Age group: 21-65 years old.
    - The procedure expected to be completed within 2 hours.
  - Exclusion Criteria:*
    - Patients with expected difficult airway management.
    - Hemodynamically unstable patients.
    - Persistent cough or high airway secretions.
    - Severe Emphysema or clinical signs of active infectious disease.
    - Hypoxemia (PaO2 <60 mmHg) or hypercarbia (PCO2 >50 mmHg)
    - Coagulopathy (INR >1.5).
    - Obesity (BMI >30 Kg/m^2).
    - Infection at the injection site, allergy to local anesthetics.
    - Neurological disorders: seizures, intracranial mass or brain edema.
- **Sampling Method:** Randomized sampling by a computer generated random numbers table.
- **Sample Size:** 40 patients.

Sample size was calculated using PASS 11 program for sample size calculation and according to the (*Pompeo et al., 2004*) study, the mean PaO2 perioperatively in the awake group =  $-3 \pm 1.5$  mmHg and in the second group =  $-6.5 \pm 1.83$  mmHg. Sample size of 40 cases per group (total 40) can detect this difference with power 100% and  $\alpha$ -error 0.05.

- **Ethical Considerations:** Approval of the research ethical committee of faculty of medicine, Ain Shams University will be obtained and informed written consents will be taken from all the participants. The thoracic epidural placement will be performed by the most experienced person of the study team.

- **Study Tools:**

- **Anesthetic sheet.**

- **Visual analogue scale:** The Visual Analogue Scale (VAS) consists of a 10 cm straight line with the endpoints defining extreme limits of 'no pain at all' (0 cm) and 'pain as bad as it could be' (10 cm). The patient is asked to mark his pain level on the line between the two endpoints. The distance between 0 and the mark then defines the subject's pain score.

- **Anesthetic plan:**

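### The primary outcome has two unranked blood-gas variables at about 13–14 times and no deciding summary, test or success rule, so the stated 0.05 cannot be shown to hold

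*Combined protocol and SAP*

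**What the plan says.** All places are in section 3 (Methodology) of the combined protocol and SAP.

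- **Primary outcome.** The outcome is change in blood gases, timed "Immediately before operation, intraoperatively per hour, and postoperatively per 2 hrs till 24h". Two variables follow without ranking: "Ratio of arterial oxygen tension to fraction of inspired oxygen" and PaCO2. A sentence beginning "Hypoxemia is defined as peripheral oxygen saturation" comes next.
- **Inclusion criteria.** "The procedure expected to be completed within 2 hours", which bounds the expected number of hourly intraoperative samples.
- **Statistical Analysis.** Means with SD, medians with range, or counts with percentages will be presented. The inferential plan is "Suitable analysis will be done according to the type of data obtained", and P<0.05 "will be considered significant".
- **Sample Size.** The calculation uses one figure per group, starting from "the mean PaO 2 perioperatively in the awake group": −3 (SD 1.5) mmHg against −6.5 (SD 1.83) mmHg, at an alpha-error of 0.05.

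**The concern.** An alpha of 0.05 describes a particular decision rule. Here the plan gives the threshold but not the rule. It does not say which of the two variables decides, or whether one is enough or both are needed. It does not say how a patient's repeated samples become one value, whether change means a change score or a baseline-adjusted comparison, or which test is used.

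Several analyses would fit the text equally well, and they carry very different false-positive rates. If the choice is made after the data are seen, a reader of the report cannot tell a planned primary result from one picked out of a couple of dozen. That cannot be credibly repaired afterwards.

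**Working it through.** **1. The plan's own figure.** Difference = 6.5 − 3 = 3.5 mmHg. Pooled SD = √((1.5² + 1.83²)/2) = 1.673. Standardised difference = 3.5/1.673 = 2.09. With 20 per group, a two-sided t test at 0.05 has power 99.9996%; with 30 per group it is higher still. The stated 100% reproduces, but for a single PaO2 comparison.

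**2. Number of comparisons.** Postoperative samples: 24/2 = 12. Intraoperative samples: 1–2 if surgery lasts 1–2 hours. Post-baseline times: 13–14. With two variables: 2 × 13 = 26 to 2 × 14 = 28. A shorter or longer operation, or a sample at hour 0 after surgery, shifts this by about one time.

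**3. One test per variable.** Assume no effect on either variable and bivariate normal test statistics with correlation r, each tested two-sided at 0.05.

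- Either significant: 1 − P(|Z1| < 1.96 and |Z2| < 1.96). At r = 0 this is 1 − 0.95² = 0.0975.
- Both significant: 0.05 + 0.05 − P(either).

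| r | either counts | both required |
|---|---|---|
| 0 | 9.75% | 0.25% |
| 0.3 | 9.5% | 0.5% |
| 0.6 | 8.8% | 1.2% |
| 0.9 | 7.0% | 3.0% |

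The both-required rate cannot exceed 5% at any r.

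**4. Every time tested, any hit counts (conditional illustration).** The documents give no correlations, so these are assumed: 0.5–0.95 between a patient's samples, either constant or first-order autoregressive, and 0.3 between the two variables. Change scores are used because the outcome is change. Null data were simulated with t tests at two-sided 0.05, 13 and 14 times, and 20 and 30 per group.

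- Constant correlation: about 54–59%. The assumed value hardly matters, because two changes from the same baseline have covariance 1 − ρ and variance 2(1 − ρ), so they correlate at 0.5 whatever ρ is.
- Autoregressive: about 40–55%, lower as the correlation rises.
- Sensitivity: with correlation 0.8 between the variables (20 per group, 14 times), 48–50% and 35–47%.
- Reference, all tests independent: 1 − 0.95^26 = 73.6%; 1 − 0.95^28 = 76.2%.

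Monte Carlo error is about 0.8 percentage points (√(0.25/4000) = 0.0079 at 4,000 replicates).

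**5. A fixed rule.** Take the mean of all post-baseline samples, adjust for the pre-operative value, and test the two variables in sequence at 0.05. Simulated error is 4.6–5.8% (Monte Carlo SE √(0.05 × 0.95/4000) = 0.34%), consistent with 5%. The same summaries with either variable counting at 0.05 give 8.8–10.6%, in line with step 3.

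**The case against.** **The sample-size paragraph points to a primary analysis.** This stands in part. Negative planning means can only be changes, and there is one oxygenation figure per group at alpha 0.05. So the paragraph suggests change scores, with oxygenation leading. But it sizes PaO2, which is not one of the two listed variables; it gives no window beyond the perioperative period; and it names no test for the trial data.

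**Nobody said any hit would count.** Correct. A reader might infer that the trial's error rate is 40–59%, or that alpha is definitely not protected. The documents support neither. They do not adopt an any-hit rule, they give no correlations, and a both-required rule would hold the error at or below 5%. What can be said is that control at 0.05 cannot be verified.

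**Hypoxemia could be taken as a third primary component.** It sits within the primary-outcome text, so a reader might add it to the count. It is better read as an explanatory definition, as bradycardia, hypotension and hypertension are defined under the circulatory outcome. Hypoxemia also appears as a complication to be observed and, when persistent, as a trigger for transfer to the other group. No error rate should be attached to it.

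**The estimator and testing order are matters of preference.** This also stands. The need to prespecify follows from the plan's own alpha; the particular model does not.

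**Conclusion.** The concern holds: as written, the plan does not allow its 0.05 to be checked. The most modest either-counts reading, one test per variable, gives 7–10% for correlations from 0.9 down to 0. Requiring both gives at most 5%. The 40–59% range is only an illustration. It rests on three assumptions: change scores, within-patient correlation 0.5–0.95 and between-variable correlation 0.3, and on a rule the plan leaves open. It moves if those assumptions move. All rates assume no effect on either variable.

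Two neighbouring matters are separate points and are not settled here: the mismatch between the sizing variable and the primary variables, and the population to be analysed.

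**What to change.** Before outcome data are examined, replace the general analysis sentence, as it applies to the primary outcome, with:

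> For each of PaO2/FiO2 and PaCO2, the mean of each patient's post-baseline samples over one prespecified window [sponsor to state] will be compared between groups by linear regression with the pre-operative value as covariate, two-sided, and reported as a difference with 95% CI. The variables will be tested in fixed sequence at 0.05, PaO2/FiO2 first, and PaCO2 only if PaO2/FiO2 is significant. Individual time points, and hypoxemia as number and percentage per group, will be descriptive.

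The sponsor may prespecify the other order.

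**Cost.** No new data are needed, since the pre-operative and later samples are already scheduled. The downsides are:

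- No confirmatory claim can be made at a single time.
- In a mean over all samples, intraoperative values carry little weight (1/13 = 7.7% to 2/14 = 14.3%), so an intraoperative difference would be diluted. A postoperative-only window would narrow the perioperative question.
- Nothing can be claimed for the second variable if the first fails.
- The documents give no SD for either listed variable, so power for the new analysis cannot be stated from them.

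The simulated 4.6–5.8% applies only to the baseline-adjusted mean of all samples. Other windows, and missed samples, were not simulated.

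### Hypoxemia is defined only on room air, so desaturation on oxygen goes uncounted, and the transfer rule has no on-oxygen threshold or duration (minor)

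*Combined protocol and SAP*

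**What the plan says.** All references are to the combined protocol and SAP; except where noted, they are to section 3 (Methodology).

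- **Definition (Primary outcome).** Hypoxemia is SpO2 "< 92% on room air with a need for oxygen supplementation". The outcome it sits under is measured before surgery, hourly during it, and two-hourly to 24 hours afterwards.
- **Oxygen rule (Study Interventions).** When SpO2 falls, "supplemental oxygen will be given to keep SpO 2 above 94"%. No starting level is given, and the rule is not limited to one arm.
- **Transfer rule (thoracic epidural group).** "In case of persistent hemodynamic instability or persistent hypoxemia, the patients will be transferred to the other group". No SpO2 level, inspired oxygen or duration is attached.
- **Complications (Study Interventions).** Patients are observed for "hypotension, bradycardia, hypoxemia, nausea, vomiting or any other adverse effects and will be managed".
- **Statistical Analysis.** Results are shown "as numbers and percentage for qualitative data".
- **Exclusion criteria.** Hypoxemia appears here as PaO2 below 60 mmHg, with no room-air condition. This governs eligibility only.
- **Inspired oxygen.** Group B is preoxygenated with 100% oxygen, but its inspired fraction during one-lung ventilation is not stated. Nothing is stated about routine oxygen for the awake arm.

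**The concern.** The definition depends on the patient breathing room air, while the oxygen rule takes a desaturating patient off room air. The rule's target (above 94%) is higher than the case limit (92%), so oxygen may be started before the limit is reached. From then on, no fall in SpO2, however deep, meets the definition. A ventilated patient given more than air is outside it throughout surgery.

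Two things are at stake. The first is complication counting: a hypoxemia rate would omit patients who desaturate despite oxygen, who may be the more severely affected. The second is consistency of conversion. The transfer rule decides when an awake patient is given general anesthesia, and section 2 makes the feasibility of awake surgery an aim. If each clinician chooses the level and the waiting time, the number of conversions is hard to interpret.

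**Working it through.** The plan gives no figure for hypoxemia frequency or for patients missed, so there is nothing to reproduce. The check is a reading of the rules together, followed by two illustrations of size.

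**1. Who is a case?** The SpO2 values are examples chosen to fall either side of the limits.

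| Patient | Case under the definition? |
|---|---|
| Falls to 91% on room air and is given oxygen | Yes; the later oxygen does not undo it |
| Given oxygen at 93%, later falls to 88% on oxygen | No |
| Group B, ventilated with more than air, falls to 88% | No |
| Group A, on oxygen from the start, falls to 88% | No |

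The gap is therefore confined to patients already on oxygen when they first cross 92%.

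**2. Is the gap equal between arms during surgery?** That depends on two unstated inputs.

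- If Group B receives more than air and Group A starts on room air, Group B counts 0 and Group A can count events.
- If both arms receive oxygen from the start, both count 0 and the count is uninformative rather than unequal.

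**3. Size for transfers.** The Introduction describes paradoxical breathing as "increasing the risk of hypoxemia and hypercapnia, sometimes so evident to require a switch to general anesthesia, in 1% of patients". Arm size is uncertain. The Sample Size entry reads "Sample size of 40 cases per group (total 40"), which gives 20 or 40 per arm; Study Interventions has two groups, "each consisting of 30 patients, namely group A and group B". At 1%, expected transfers are 0.01 × n, and the chance of at least one is 1 − 0.99^n.

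| n per arm | Expected transfers | P(at least one) |
|---|---|---|
| 20 | 0.2 | 1 − 0.99^20 = 18% |
| 30 | 0.3 | 1 − 0.99^30 = 26% |
| 40 | 0.4 | 1 − 0.99^40 = 33% |

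**4. Size for a by-arm count, in the unfavourable case.** Assume that Group B is fixed at 0 by the definition. With equal arms and x v 0 patients with an event, the two-sided Fisher exact p is 2·C(n,x)/C(2n,x).

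| n per arm | Largest non-significant result | Smallest result with p < 0.05 |
|---|---|---|
| 20 | 4 v 0, p = 0.106 | 5 v 0 (25%), p = 0.047 |
| 30 | 5 v 0, p = 0.052 | 6 v 0 (20%), p = 0.024 |
| 40 | 5 v 0, p = 0.055 | 6 v 0 (15%), p = 0.026 |

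Now suppose the true intraoperative desaturation rate is the same in both arms and the definition captures none of it in Group B. The chance of a spurious p < 0.05 then depends on the assumed rate and on the share of Group A patients with an event who are captured. The rates and shares are assumptions and are not in the documents.

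| Assumed true rate | 30 per arm, all captured | 30 per arm, half captured | 20 per arm, all captured |
|---|---|---|---|
| 10% | 7% | 0.3% | 4% |
| 20% | 57% | 7% | 37% |
| 30% | 92% | 29% | 76% |

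If no Group A events are captured, because those patients are also on oxygen throughout, the chance is 0.

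**The case against.** The strongest reply is that little of the planned analysis uses this definition. No hypoxemia rate is a listed endpoint. By-arm reporting is an inference from its being defined, listed among the complications, and qualitative data being shown as counts and percentages. The primary variables are PaO2/FiO2 and PaCO2; neither uses the definition, and the ratio already takes inspired oxygen into account. All of this stands and keeps the point small.

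A reader might infer that the transfer rule cannot operate, because a patient on oxygen can never be hypoxemic as defined. The documents do not support that. The definition sits under the outcome and is not tied to the transfer rule. Read after the oxygen rule, persistent hypoxemia naturally means hypoxemia that oxygen has not corrected. An arterial line is also in place, so clinicians have PaO2 at any inspired oxygen. What remains is that level and duration are left to judgement.

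A reader might also infer that any intraoperative count must be unequal and biased against the awake arm. That needs inspired oxygen above air in Group B and room air in Group A, and the protocol states neither.

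The PaO2 limit of 60 mmHg in the exclusion criteria is a second definition of hypoxemia. Since it governs only entry to the trial, it does not fill the gap.

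**Conclusion.** The point holds, at minor severity. The stated definition cannot capture desaturation in a patient already on oxygen, so any hypoxemia count would be incomplete. How incomplete cannot be estimated from the documents.

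Inequality between arms during surgery is possible but not established. If Group B has more than air and awake patients start on room air, the intraoperative count is loaded against the awake arm and could not create a false benefit for it. A false significant difference would then need events in 15% to 25% of awake patients, and no document supports rates that high. After surgery the gap can affect either arm, with nothing to show that it differs.

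The transfer rule is workable but imprecise. At the cited 1%, a figure for hypoxemia and hypercapnia together, fewer than one transfer is expected at any of the three arm sizes. The primary PaO2/FiO2 and PaCO2 comparisons are unaffected by the definition.

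**What to change.** - **Definition.** In both arms, define hypoxemia as SpO2 below 92% at any inspired oxygen.
- **Recording.** With each event, record the inspired oxygen and any start or increase of oxygen.
- **Reporting.** If hypoxemia is reported by arm, count patients with at least one event and read the count alongside PaO2/FiO2.
- **Transfer rule.** Define persistent hypoxemia as SpO2 below the same limit despite supplemental oxygen, for a duration that the investigators set in advance.

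The cost is two wording changes and a few fields on the anesthetic sheet; pulse oximetry is already in place. There are two downsides. The reported hypoxemia rate will be higher. A common SpO2 limit also does not make the arms fully comparable, because the same SpO2 at a higher inspired oxygen means worse gas exchange. PaO2/FiO2 should therefore remain the oxygen-adjusted comparison.
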